8.1.5. Intercurrent Event Strategies (IES) for Time to Event Analysis

For each time to event analysis, one of the intercurrent event strategies (IES) provided in Table 5 will be specified for the estimand.

Table 5: Intercurrent Event Strategies (IES) for Time to Event Analyses

IES Policy 1	IES Policy 2 (Note: Differences from Policy 1 are in blue text.)

Participants who terminate early from the study prior to endpoint will be censored at the time of early termination.	
For participants who terminate early from the study prior to endpoint and have consented to be contacted via phone,
a participant-reported diagnosis of RA that was treated will be counted as a case of CL-RA/IA at the time of initiation of the RA medications.For participants without a reported RA diagnosis, data will be censored at the date of last phone contact.For participants who terminate early from the study prior to endpoint and cannot be contacted, data will be censored at the time of early termination.

Participants who choose to take off-study HCQ on a continuous basis prior to endpoint will be censored at the time this therapy began.⁺	
Participants who choose to take off-study HCQ on a continuous basis prior to endpoint will not be censored at the time this therapy began.⁺

Participants who were diagnosed with RA by an outside physician and started prohibited medications will be censored at the time the medications were started, if started prior to endpoint.[*] Only cases where the data collected on-study (at a study visit) meet the study-defined endpoint definition will count as CL-RA/IA in the analysis.	
Participants who were diagnosed with RA by an outside physician and started prohibited medications prior to endpoint will be included in the analysis as having developed CL-RA/IA at the time the prohibited medications were initiated, regardless of whether or not the diagnosis can be confirmed using study-defined endpoint criteria and study data.^{&}

Participants who started prohibited medications during study participation to treat conditions other than RA will be censored as follows:
If a participant is taking a prohibited medication other than corticosteroids, per protocol section 5.6, then time-in-study will be censored at the start of the first prohibited medication.	
Participants who started prohibited medications during study participation to treat conditions other than RA will be censored as follows:
If a participant is taking a prohibited medication other than corticosteroids, per protocol section 5.6, then time-in-study will be censored at the start of the first prohibited medication.

IES Policy 1	IES Policy 2 (Note: Differences from Policy 1 are in blue text.)

 ○ If a participant is taking corticosteroids, then time-in-study will be censored at the time when the permitted conditions in protocol section 5.5 are violated. 	
 ○ If a participant is taking corticosteroids, then time-in-study will be censored at the time when the permitted conditions in protocol section 5.5 are violated. ● For participants who terminate early from the study prior to a diagnosis of RA and have consented to be contacted via phone, data for a participant who reports use of a prohibited medication to treat conditions other than RA will be censored at the time the prohibited medication was started.

 ● Participants who discontinue study-provided HCQ/placebo prematurely or who are not compliant with planned dosing will be included in the analysis and will not be censored at the time of study drug discontinuation or noncompliance. 	
 ● Participants who discontinue study-provided HCQ/placebo prematurely or who are not compliant with planned dosing will be included in the analysis and will not be censored at the time of study drug discontinuation or noncompliance.

+ Participants who took off-study HCQ (HCQ not provided by the study) continuously for at least 4 weeks prior to meeting the endpoint were censored at the time of starting the off-study HCQ

* Participants who were diagnosed with RA by an outside physician and did not start prohibited medications prior to endpoint were not censored at the time of the RA diagnosis.

& Participants who were diagnosed with RA by an outside physician and did not start prohibited medications prior to endpoint were not classified in the analysis as having developed CL-RA/IA.

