4.3.3 Rheumatology Clinics

Individuals who are anti-CCP positive in the absence of IA (with testing typically performed by primary care providers for evaluation of non-inflammatory musculoskeletal pain) are evaluated regularly and with increasing frequency in rheumatology clinics, raising an important clinical

issue regarding how to manage these patients, and potentially prevent them from developing clinically-apparent RA. Importantly, in discussion with multiple clinicians these patients are on occasion being treated with HCQ if they have symptoms that are interpreted as related to RA, even in absence of IA. Therefore, formalizing the benefit of this therapy could lead to a significantly improvement in clinical care.

Briefly, these subjects will be identified through IRB-approved means including screening clinic registries and medical records, and making practitioners aware of this clinical trial. Individuals meeting inclusion criteria will be approached for trial screening and enrollment.

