8.3.1 Efficacy Analysis

8.3.1.1 Primary Efficacy Analysis

The primary efficacy analysis is designed to test the hypothesis that HCQ will slow or prevent the onset of clinically-apparent RA in high-risk subjects. The analysis will be based on the KM estimated risk of clinically-apparent RA at 36 months. The KM curves will be plotted along with 95% confidence intervals. The null hypothesis, “H0: survival at 3 years is equal across arms”, will be tested against the two-sided alternative with $\alpha=0.05$. The test statistic will be a Wald-type chi-square statistic derived by dividing the difference of the logit-transformed KM survival estimates for each arm by the associated variance derived using the delta-method. The logit-transformed Wald-type chi-squared statistic has better test performance than the untransformed version in that the nominal Type I error is better retained. Subjects who choose to take off-study HCQ on a continuous basis will be censored at the time this therapy begins. This analysis will ignore stratification by site and method of recruitment, because the unstratified test statistic has been shown to have better test performance [177].

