8.2.2. Primary Estimand of the Primary Clinical Endpoint

The primary estimand for the primary clinical endpoint of the development of clinically-apparent RA (CL-RA) at 36 months will be analyzed according the following specifications:

Table 7: Primary Estimand of Primary Objective

Variable: Time to development of CL-RA	
Estimand Label: Primary 1.0	
Population: mITT	IES Policy 1
Population Level Summary (PLS): Estimated risk at 36 months for each treatment arm and the difference between the treatment arms (with 95% confidence intervals) will be derived from Kaplan-Meier (KM) curves and using the Greenwood formula for estimating the variance.	Analysis: The analysis will be based on the KM estimated risk of CL- RA at 36 months, where risk = (1-KM estimated probability of “survival”). Survival for this analysis is defined as absence of CL-RA. Estimated risks will be derived from a Kaplan-Meier curve using censored time-to-event data to account for attrition under the assumption of non-informative censoring. The test statistic will be a Wald-type chi-square statistic derived by dividing the difference of the logit-transformed KM survival estimates for each arm by the associated variance derived using the delta-method. (Klein, et al. 2007)) [2]

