5.2. Primary Estimand

5.2.1. Definition

The primary objective of the study is to determine the efficacy of a 12-month course of HCQ to prevent the development of clinically-apparent RA at 36 months in participants at high-risk for future RA due to high titer elevations of anti-CCP3 (≥ 40 units) but who are without a history or clinical findings of IA at Baseline. For this study, clinically-apparent RA will be defined using the 2010 ACR/EULAR Classification Criteria as either:

- (1) A score of ≥ 6 defining “definite RA” or
- (2) A joint examination consistent with RA-like synovitis with ≥ 1 erosion identified via x-ray imaging of the hands, wrists, and feet.

The primary hypotheses to be evaluated at interim and end-of-study analyses are:

H0: RA-free survival at 3 years (36 months) is equal across arms;

HA: RA-free survival at 3 years (36 months) is not equal across arms.

Variable:

Time to development of clinically-apparent RA

Population:

The mITT population will be used for these analyses.

Intercurrent Events Strategies (IES):

1. Participants who terminate early from the study prior to a diagnosis of RA will be censored at the time of early termination.
2. Participants who choose to take off-study HCQ on a continuous basis will be censored at the time this therapy began.

The rationale for this decision is that our ability to evaluate the impact of a short 12-month course of HCQ on development of RA is confounded if individuals choose to take HCQ, provided by physicians outside of the study. Further, data for individuals assigned to 12-months of placebo and then take off-study HCQ could further confound results.

3. Participants who were diagnosed with RA by an outside physician and started prohibited medications will be censored at the time the RA medications were started. Only cases where data collected on-study confirm the diagnosis using the study-defined primary endpoint definition will count as RA/IA cases in the primary analysis.
4. Participants who started prohibited medications during study participation to treat conditions other than RA will be censored as follows:
 - o If a participant is taking a prohibited medication other than corticosteroids, then time-in-study will be censored at the start of the first prohibited medication.

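### The 4-week footnote to SAP Table 5 lets the next 28 days decide whether an off-study HCQ user is censored at the start date, which shifts the Kaplan-Meier risk up by a small amount

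*SAP*

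**What the plan says.** Primary 1.0 (SAP 8.2.2) estimates the 36-month Kaplan-Meier risk of CL-RA in the mITT population under intercurrent event Policy 1, "using censored time-to-event data to account for attrition under the assumption of non-informative censoring".

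Four places deal with off-study HCQ:

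- Protocol 8.3.1.1: "Subjects who choose to take off-study HCQ on a continuous basis will be censored at the time this therapy begins".
- Interim SAP 5.2.1 (SAP Appendix 14.1): "Participants who choose to take off-study HCQ on a continuous basis will be censored at the time this therapy began".
- SAP 8.1.5, Table 5, Policy 1 cell: continuous users before endpoint "will be censored at the time this therapy began".
- SAP 8.1.5, Table 5, footnote +: those who took it "continuously for at least 4 weeks prior to meeting the endpoint were censored at the time of starting the off-study HCQ".

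The first three do not define continuous use. The footnote does, as at least 4 weeks before the endpoint, and it keeps the start date as the censoring date. The same + mark sits on the Policy 2 cell, which says these participants are not censored. SAP section 12, which lists changes from the protocol, does not mention the 4-week condition.

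Two other Policy 1 bullets censor at the start of a prohibited medication with no 4-week condition. One covers an outside RA diagnosis, the other conditions other than RA. HCQ is on the prohibited list in protocol 5.6. Table 5 does not say which rule takes precedence.

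**The concern.** A valid censoring time uses only what is known by that time. Here, status on the day HCQ starts is settled by the following 28 days. Take three participants who start off-study HCQ on day 500:

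- CL-RA on day 520: not censored, counted as an event.
- Still taking it and event-free on day 528: censored back to day 500, so 28 event-free days leave the risk set.
- Still taking it, CL-RA on day 600: censored at day 500, event not counted.

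The first 28 days after starting thus keep their events but lose the event-free time of those who continue. This makes the censoring informative by construction, even if starters have the same hazard as everyone else.

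The rule reaches Primary 1.0, Sensitivity 1.2 and all secondary time-to-event estimands (2.1 to 6.1), since all use Policy 1. With 144 randomized and an even split assumed, one event in an arm of 72 is worth about 1/72 = 1.4 points.

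**Working it through.** **Inputs from the documents.** Control risk 50% and HCQ risk 25% at 3 years, exponential onset, 80 per arm, 20% attrition (protocol 8.1); two-sided alpha 0.05 (protocol 8.3.1.1); 144 randomized (Interim SAP 5.2.2.1).

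**Assumptions.** The documents give neither the number of off-study HCQ starters nor their hazard. Uptake was set at 5-30% by 3 years in the absence of onset (20% gives about 21 actual starters per 144 at 50% risk). The hazard in the first 4 weeks after starting was set at 1, 5 or 10 times baseline.

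**Step 1: the plan's own figures.** The hazards are -ln(0.50)/3 = 0.231 and -ln(0.75)/3 = 0.096, ratio 2.41, as stated. Simulating the logit Kaplan-Meier test with 80 per arm gives 90.9% power (two-proportion formula 91.2%; stated 90%). The model matches the plan's.

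**Step 2: hand example.** Forty are at risk and 5 start HCQ together. One meets the endpoint at week 2; 4 continue event-free. The Kaplan-Meier factor at week 2 is:

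- footnote: 4 removed at start, 1 - 1/36 = 0.972
- censor continuing users at start + 28 days: 1 - 1/40 = 0.975
- censor all at start: no event, 1.000

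**Step 3: direction.** Against start + 28 days, the footnote keeps the same events and shrinks the risk set, so survival falls or stays the same. Against censoring continuous users at start, it turns some censored observations into events before month 36, which also can only lower survival or leave it unchanged. Starters who stop before 4 weeks are not censored under the footnote and keep all their follow-up.

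**Step 4: size.** Kaplan-Meier risk at 36 months (%), 400,000 simulated subjects per row, 50% base risk. Differences were taken before rounding.

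| Uptake | Early hazard | No HCQ censoring | Start | Start + 28 d | Footnote | Footnote minus start + 28 d | Footnote minus start |
|---|---|---|---|---|---|---|---|
| 5% | 1x | 50.02 | 50.06 | 50.07 | 50.11 | 0.04 | 0.05 |
| 5% | 10x | 50.47 | 50.12 | 50.50 | 50.54 | 0.04 | 0.41 |
| 20% | 1x | 49.94 | 49.93 | 49.94 | 50.13 | 0.20 | 0.20 |
| 20% | 10x | 51.55 | 50.07 | 51.68 | 51.85 | 0.17 | 1.78 |
| 30% | 1x | 50.03 | 50.03 | 50.03 | 50.34 | 0.31 | 0.32 |
| 30% | 10x | 52.19 | 50.02 | 52.54 | 52.80 | 0.27 | 2.78 |

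The second-last column isolates conditioning on the future: 0.04 to 0.31 points at 50% risk, and 0.03 to 0.20 at 25% risk. If only half of starters persist, the 20% uptake figures fall to 0.09 (1x) and 0.08 (10x). The last column also contains real events in days 0-28, which the start + 28 day rule counts as well.

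**Step 5: the test.** With 72 per arm, 20% loss, 50% risk in both arms and 4,000 trials, rejection under the footnote was 5.1-5.2% with 10% uptake in each arm. With uptake of 5% against 20% it was 5.4% (1x) and 5.9% (10x), against 5.1% and 5.2% for censoring at start. The Monte Carlo standard error is √(0.05 × 0.95/4000) = 0.34 points, so these rates are not clearly different. The mean Z did move in the 10x unequal case, from 0.001 to 0.135; at 1x it did not (0.016 and 0.015).

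**The case against.** The strongest reply is that censoring at start is the wrong yardstick. If symptoms prompt HCQ, starters already carry a higher risk, so censoring them at start is itself informative and gives too low a risk. With a raised hazard that persists after starting (6-fold and 10-fold, 14% starting), the risk without HCQ censoring is 57.1% and 58.3%. Censoring at start gives about 50.0% and the footnote 51.0% and about 51.7%. The footnote is then nearer the uncensored risk. This stands, and it is why the 1.8 or 2.8 points in the last column of the table should not be read as bias. It does not excuse the backdating, which shifts the estimate upward even at unchanged hazard.

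Policy 2 (Sensitivity 1.1 and 1.3) drops this censoring. True, but it also changes the handling of outside diagnoses and phone follow-up, so it does not isolate the footnote.

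The prohibited-medication bullets may also apply to HCQ. If they take precedence, few or no early events are kept. They do not clearly cover HCQ given for RA-type symptoms without a diagnosis, which protocol 4.3.3 describes in clinic patients as "on occasion being treated with HCQ if they have symptoms that are interpreted as related to RA, even in absence of IA". The overlap needs reconciling either way.

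A reader might infer two further things that the documents do not support:

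- **A tilt toward HCQ.** Protocol 4.3.3 describes clinic patients outside the trial and says nothing about uptake by arm. The trial was double-blind, and both arms are off study drug after month 12.
- **A threshold chosen in light of the interim results.** The 4-week cut is absent from the December 2021 Interim SAP and present in the SAP approved in May 2023, after the April 2022 interim analysis. The approval date does not show when the cut was chosen, and the footnote can be read as defining a term already in use.

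**Conclusion.** The point holds as a small defect in a stated rule. As written, footnote + makes the censoring time depend on later information, contrary to the non-informative censoring assumed for Primary 1.0, and it adds a condition that protocol 8.3.1.1 and the Interim SAP do not have. Compared with a 4-week rule that does not backdate, it can only raise an arm's risk estimate or leave it unchanged. The size is about 0.05 to 0.3 points under 5-30% assumed uptake, with all starters persisting and the footnote governing. The actual size cannot be computed because uptake is not given. The shift can occur in both arms, so the comparison is biased only if uptake or early hazard differs between them, and no direction is established. It is worth correcting because it sits in the primary estimand and the correction is cheap, not because it is likely to change the result.

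**What to change.** For Primary 1.0 and the other Policy 1 estimands, use a censoring time that depends only on information available by then. Either:

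- censor every starter at the start of off-study HCQ, the date used in the protocol and Interim SAP; or
- to keep the 4-week definition of continuous use, censor at start + 28 days those still taking it and event-free, and retain days 0-28 for everyone.

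Run the other as a sensitivity analysis, because the two are not interchangeable when early hazard is raised. At ten-fold hazard they differ by 51.68 - 50.07 = 1.6 points at 20% uptake and 52.54 - 50.02 = 2.5 points at 30%.

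Also:

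- state in Table 5 whether the HCQ rule or the prohibited-medication bullets govern when both could apply;
- remove the + mark from the Policy 2 cell, which the footnote contradicts;
- list the 4-week cut in SAP section 12;
- report by arm the number of off-study HCQ starters and the number with CL-RA within 28 days of starting.

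The cost is a reworded footnote, one line in section 12, one small table and one extra run. The first option censors a few brief users; the second adds up to 28 days of follow-up for each continuing user.

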8.2. Primary Objective

The primary objective for the ARA08 study is to determine the efficacy of a 12-month course of HCQ to prevent the development of clinically-apparent RA (CL-RA) at 36 months in participants at high-risk for future RA due to high titer elevations of anti-CCP3 (≥ 40 units) but who are without a history or clinical findings of IA at Baseline.

8.2.1. Computation of the Primary Clinical Endpoint

Individuals who have ≥ 1 swollen joint consistent with RA-like synovitis will be evaluated for presence of clinically-apparent RA.

The development of clinically-apparent RA (CL-RA) at 36 months is the primary clinical endpoint to evaluate the primary objective. CL-RA will be defined using the 2010 ACR/EULAR Classification Criteria as either:

- (1) A score of ≥ 6 defining “definite RA” or
- (2) A joint examination consistent with RA-like synovitis with ≥ 1 erosion identified via x-ray imaging of the hands, wrists, and feet.

At each clinic visit, a joint exam and physician’s assessment are conducted. If a participant presents with swollen joint(s) that are consistent with RA-like synovitis, all the items necessary to establish the fulfillment of the 2010 ACR/EULAR criteria will be ascertained (See Table 6); however, the laboratory parameters including IgM-RF, anti-CCP3 and hsCRP will be tested at a central laboratory. Due to issues regarding sample stability and test reproducibility, hsCRP will

Autoimmunity Centers of Excellence
Statistical Analysis Plan – ARA08 StopRA

be used for the calculation of the ACR/EULAR criteria and disease activity measures; ESR will not be used.

Table 6: 2010 ACR/EULAR Classification Criteria

Who should be tested? Patients with ≥ 1 swollen joint consistent with synovitis not better explained by another disease. If the patient meets these initial criteria with a score of $\geq 6/10$ they can be classified as having ‘definite RA’:	
A. Joint involvement*	
1 large joint	0
2-10 large joints	1
1-3 small joints	2
4-10 small joints	3
>10 joints (at least 1 small)	5
B. Serology (at least 1 test needed)	
Negative RF and ACPA	0
Low positive RF or ACPA	2
High positive RF or ACPA**	3
C. Acute-phase reactants (at least 1 test needed)	
Normal CRP and ESR	0
Abnormal CRP or ESR	1
D. Duration of symptoms	
<6 weeks	0
≥ 6 weeks	1

* Joint involvement refers to any *swollen* or *tender* joint on examination. Distal interphalangeal joints, first carpometacarpal joints, and first metatarsophalangeal joints are *excluded from assessment*. “Large joints” refers to shoulders, elbows, hips, knees, and ankles. “Small joints” refers to the metacarpophalangeal joints, proximal interphalangeal joints, second through fifth metatarsophalangeal joints, thumb interphalangeal joints, and wrists.

** High positive is equivalent to >3 times the upper limit of normal based on the reference range of the laboratory that assesses the biomarker.

NOTE: Patients with erosive disease typical of rheumatoid arthritis with a history compatible with prior fulfillment of the 2010 criteria should be classified as having RA.

8.2.2. Primary Estimand of the Primary Clinical Endpoint

The primary estimand for the primary clinical endpoint of the development of clinically-apparent RA (CL-RA) at 36 months will be analyzed according the following specifications:

Table 7: Primary Estimand of Primary Objective

Variable: Time to development of CL-RA	
Estimand Label: Primary 1.0	
Population: mITT	IES Policy 1
Population Level Summary (PLS): Estimated risk at 36 months for each treatment arm and the difference between the treatment arms (with 95% confidence intervals) will be derived from Kaplan-Meier (KM) curves and using the Greenwood formula for estimating the variance.	Analysis: The analysis will be based on the KM estimated risk of CL- RA at 36 months, where risk = (1-KM estimated probability of “survival”). Survival for this analysis is defined as absence of CL-RA. Estimated risks will be derived from a Kaplan-Meier curve using censored time-to-event data to account for attrition under the assumption of non-informative censoring. The test statistic will be a Wald-type chi-square statistic derived by dividing the difference of the logit-transformed KM survival estimates for each arm by the associated variance derived using the delta-method. (Klein, et al. 2007)) [2]

